## **2** Research Hypotheses

Please describe the research aims and hypotheses in the box below. To input text, click in the box below and start typing.

Note: Procedures will be explained in a separate section below.

The purpose of the proposed study is to preliminarily evaluate a technology-based information and coaching/support program, TACAD (Technology-based Information and Coaching/Support Program for Asian American women who are family caregivers of persons living with Alzheimer's Disease), in improving health outcomes of Asian American women who are family caregivers of persons living with Alzheimer's disease (AACA) and their care recipients. The **specific aims** of the study are to:

- Aim 1. Qualitatively evaluate TACAD through an expert review and a usability test.
- **Aim 2**. Quantitatively evaluate the preliminary efficacy of TACAD in improving health outcomes of AACA and their care recipients.
- -Hypothesis 1. After controlling for background and health/disease factors, the intervention group (AACA who use TACAD and the Alzheimer's Association [AA] website) will show significantly greater improvements than the

active control group (AACA who use only the AA website) in their health outcomes (stress, physical and psychological symptoms, and quality of life) and their care recipients' health outcomes (activities of daily living, behavioral and psychological symptoms, mood status, and quality of life) from baseline (pre-test) to Time Points 1 (post 1 month) and 2 (post 3 months).

- -Hypothesis 2. After controlling for background and health/disease factors, the intervention group will show significantly greater improvements than the control group in caregiving experience (caregiving activity, coping, caregiving competence, and caregiving skills) from baseline to Time Points 1 and 2.
- -Hypothesis 3. After controlling for background and health/disease factors, the intervention group will show significantly greater improvements than the control group in theory-based variables (attitudes, self-efficacy, perceived barriers, and social influences related to caregiving of PLAD) from baseline to Time Points 1 and 2.

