
## 4 Design and Methodology

Provide a brief description of the study design or data collection methodologies. Details regarding protocol specific research procedures will be discussed in a later section.

The study includes two phases: (a) a usability test and an expert review (Phase 1) and (b) a pilot randomized clinical trial (Phase 2). Phase 1 has been completed at Emory, and only Phase 2 will be conducted at Univ. of Texas at Austin (UT Austin). For Phase 2, the data will be collected at three points: (a) pre-test; (b) post 1 month; and (c) post 3 months. The collected data will be analyzed after the data collection of all the participants is completed.

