## 5 Data Analysis

Describe the data analysis plan, including any statistical procedures or power analysis.

The data will be randomly assigned with serial ID numbers. All tests will be assumed two-sided and an alpha level of .05 will be used. SAS 9.4 will be used for data processing and all statistical analyses. Missing data will be handled by multiple imputations of dependent values. 101–103 Analyses just of complete data will be conducted and comparisons of groups with and without missing data will be made. In addition, sensitivity analyses of complete data will be conducted and compared imputed data analysis. An **intent-to-treat** analysis will be employed. For **Hypotheses 1 to 3**, differences in continuous outcome measures over time will be examined using **linear mixed-effects modeling.** In particular, we will fit mixed effects models to each continuous outcome measure. We will use random intercepts as well as explore random slopes to represent subject level variability. Fixed-effects corresponding to group, time and group x time interaction will be included in the model. A significant group x time interaction will indicate substantial differences in the groups over time. Restricted maximum likelihood method will be used for estimation, and the most appropriate covariance structure will be examined.

Since Data and Safety Monitoring Boards (DSMBs) are required only for phase III clinical trials (NOT-OD-00-038.html), we do not include a DSMB for this intervention study. For the proposed intervention study, we have

the following data safety monitoring plan (DSMP). First, to manage and protect the data collected, only summary data will be openly accessible to funding agency or will appear in publications. Research participants will be informed that they are free to decline to answer any questions they do not wish to answer or to stop participating in the project at any time. When a participant withdraws from participation, the data that they have provided will be immediately removed. Also, the data will have no identifying information to link a subject to the data.

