#### Phase 2 (Aim 2)

All research activities in Phase 2 will be done virtually. The study website will be developed first. The study website is the Web-App of the intervention program. The website at Emory was originally developed and refined by the other PI, [name], and it is owned by [name]. As soon as the grant transfer is completed, the website will be housed at The Univ. of Texas at Austin. To access/use the program through the website, the participants will be provided with an account with ID and passwords, which they could change at their convenience. The data collected through the website will be just the data on the participants' activities in the website (e.g., how many times per week they log in and out, what components they used in the website, how many messages that they are posting) that will be used to determine the dose-response effect of the program later. The current website at Emory is: https://tacad.nursing.emory.edu Again, the website will be moved to UT- Austin once the grant transfer is completed, which requires this IRB approval.

When potential participants visit the website, they will review the "informed consent" and click "I agree to participate" if they agree. After checking them against the inclusion criteria, only those who meet the criteria will be automatically **randomized** into two groups within each sub-ethnic group using an automated random number generator through the website. The randomization will be done within each sub-ethnic group to have an adequate number of participants in each sub-ethnic group. The intervention group (Group 1) will use both TACAD and Alzheimer's Association (AA) website while the control group (Group 2) will use only AA website. The women will be asked to fill out the baseline questionnaire. Then, they will be provided with IDs and passwords to log on the website. Both groups will have an electronic instruction sheet on when they need to come back and fill out questionnaires (see the below for the instruments) and/or use TACAD (see the below for more information on TACAD). Also, both groups will use the AA website (see the below for more information on the website) for 3 months. Only the intervention group will use TACAD for 3 months. Basically, they need to use TACAD and/or the AA website whenever they want to use; no requirement for reimbursement. They are recommended to visit the

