Instruments. The instruments to measure caregivers' health outcomes (primary outcomes; Hypothesis 1) include: (a) Multidimensional Caregiver Strain Index, Perceived Stress Scale, Acculturation Stress Scale (ASS), 148 and Social Readjustment Rating Scale (SRRS)  (to measure stress); (b) the Women's Symptom Index (to measure physical and psychological symptoms); and (c) EQ-5D-5L(to measure the quality of life). The instruments to measure care recipients' health outcomes (primary outcomes; Hypothesis 1) will include: (a) Informant Questionnaire on Cognitive Decline in the Elderly (IQCODE)(to measure the cognitive status of care recipients); (b) Lawton ADL/IADL Scale (to measure PLAD's activities of daily life); (c) Revised Memory and Behavior Problem Checklist (to measure behavioral and psychological symptoms of care recipients); (d) Neuropsychological Inventory Questionnaire (to measure care recipients' mood status); and (e) Quality of Life Scale in Alzheimer's Disease (to measure care recipients' quality of life). The instruments to measure caregiving experience (secondary outcomes; Hypothesis 2) will include: (a) Caregiver Activity Survey (to measure caregiving activity); (b) Ways of Coping Scale (to measure coping); (b) Pearlin Mastery, Loss, and Competence Scale (to measure caregivers' mastery of caregiving competence); and (c) Caregiver Assessment of Behavioral Skill Scale (to measure caregiving skills). 163 The theory-based variables (attitudes, self-efficacy, perceived barriers, & social influences; Hypothesis 3) will be measured using the modified Questions on Attitudes, Subjective Norm, Perceived Behavioral Control, and Behavioral Intention (QASPB). 164 Covariates that will be considered in determining the effect of TACAD on outcome variables include caregivers' sociodemographic characteristics and caregiving history (e.g., socioeconomic status, PLAD information, length of caregiving, co-residence with recipient). The reliability and validity of all the instruments have been established among Asian Americans. Cronbach's alpha of the instruments ranged from .70 to .96 among Asian Americans. Because no existing instruments have culture-specific measures, we will add open ended questions to all the measures to explore culture specific aspects that are missing in the specific measures. The same questionnaire will be used at the three time points except the questions on sociodemographic characteristics and caregiving history (e.g., socioeconomic status, PLAD information, length of caregiving, co-residence with recipient). The questions on sociodemographic characteristics and caregiving history (e.g., socioeconomic status, PLAD information, length of caregiving, co-residence with recipient) will be asked only at the pre-test. This has been clarified on p. 10.

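### Section 5 tests efficacy by a valid group x time interaction that amounts to a change-score comparison; adjusting for the collected baseline and naming the randomisation stratum would improve it at almost no cost

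*Combined protocol and SAP*

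**What the plan says.** Section 5 fits a linear mixed model to each continuous outcome: "Fixed-effects corresponding to group, time and group x time interaction will be included in the model". The decision rule is "A significant group x time interaction will indicate substantial differences in the groups over time". Random intercepts are planned and random slopes are to be explored. Section 5 does not say whether time is categorical or linear in months. It names no visit contrast, does not adjust for the baseline outcome, and names no term for the randomisation stratum.

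Section 2 (Research Hypotheses) frames the effect as improvement "from baseline (pre-test) to Time Points 1 (post 1 month) and 2 (post 3 months", that is, at two named visits. It also promises adjustment: "After controlling for background and health/disease factors, the intervention group will show significantly greater improvements than the control group". The Instruments paragraph of Phase 2 (Aim 2) refers to "Covariates that will be considered in determining the effect of TACAD on outcome variables" and gives examples, which include neither sub-ethnic group nor the baseline outcome.

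On randomisation, Phase 2 (Aim 2) states: "The randomization will be done within each sub-ethnic group to have an adequate number of participants in each sub-ethnic group". Section 17 confirms the two strata, Chinese and Korean. In the Phase 2 narrative, the step after randomisation and the description of the arms is "The women will be asked to fill out the baseline questionnaire".

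**The concern.** On the natural reading, the pre-test is one of the three modelled time points and the group main effect is free. The interaction contrasts then subtract each woman's baseline in full. Randomisation makes the baseline group difference zero in expectation, provided the baseline is not affected by allocation. Regressing on baseline is then at least as precise as subtracting it, and strictly more precise for any correlation below 1.

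This matters because Section 15 cuts the trial from a calculated 105 per group to 30 per group, and the aim is preliminary efficacy. What such a trial can deliver is mainly an estimate with an interval, and the planned model gives a wider interval than the same data allow. Two specification gaps sit beside this: the coding of time, which determines which quantity is tested, and the stratum used to randomise.

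**Working it through.** **The plan's own figure.** Section 15 sizes on a difference of 0.5 between follow-up means, 80% power, alpha 0.00625. With SD 1 (assumed; none is stated), a two-sided two-sample t calculation gives 105 per group (power 0.804), so the figure reproduces. At 30 per group and alpha .05 the same calculation gives 48%. It contains no baseline term and no interaction, so it does not describe the Section 5 test.

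**Inputs.** From the documents: 30 per arm (Section 15), two-sided alpha .05 (Section 5), visits at 0, 1 and 3 months (Section 4). Assumed: SD 1, compound symmetry with correlation rho from .3 to .8, complete data, and effects of up to 0.5 SD.

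**Variance at one visit** (times 2/n for the group contrast):
- change from baseline: 2(1-rho) = 1.40/1.00/0.60/0.40 at rho .3/.5/.7/.8
- baseline-adjusted: 1-rho^2 = 0.91/0.75/0.51/0.36
- ratio (1+rho)/2 = 0.65/0.75/0.85/0.90

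**Joint 2-df test.** Let e be the vector of effects at months 1 and 3. The noncentrality is e'V^-1 e.
- Planned: V = (2/30) times a matrix with diagonal 2(1-rho) and off-diagonal (1-rho); F with 2 and 57 df.
- Adjusted: V = (2/30)(1+1/56) times a matrix with diagonal 1-rho^2 and off-diagonal rho-rho^2; F with 2 and 56 df. The factor 1+1/56 charges for estimating the baseline slope.

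Worked at rho .5 with e = (0.5, 0.5). Planned: 15/0.75 x 0.25 = 5.00, power 48%. Adjusted: 15 x (56/57)/0.5 x 0.25 = 7.37, power 65%.

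| Effect (month 1, month 3) | Planned, rho .3/.5/.7/.8 | Adjusted | Gain (points) |
|---|---|---|---|
| Sustained (0.5, 0.5) | 36/48/71/88% | 60/65/80/92% | 24/17/9/4 |
| Build-up (0.25, 0.5) or fade (0.5, 0.25) | 28/37/58/77% | 43/49/65/80% | 15/11/7/4 |
| Month 3 only (0, 0.5) | 36/48/71/88% | 42/52/73/89% | 6/4/2/0.6 |

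A simulation of 8,000 trials per cell for the sustained effect gave .360/.483/.715/.880 planned and .605/.665/.805/.921 adjusted. Null rejection was between .046 and .055. Using 116 rather than 57 denominator df for the planned test moves its power by only about 1 point.

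**Month-3 95% half-width.** Change: t(58) x sqrt((2/30) x 2(1-rho)) = 0.61/0.52/0.40/0.33 SD. Adjusted: t(57) x sqrt((2/30)(1-rho^2)(1+1/56)) = 0.50/0.45/0.37/0.31 SD.

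**Time coding, without baseline adjustment** (rho .3/.5/.7/.8; linear uses months 0, 1, 3 with 1 and 117 df):

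| Effect | Linear, 1 df | Categorical, 2 df |
|---|---|---|
| Sustained | .294/.389/.581/.755 | .358/.482/.712/.879 |
| Build-up | .357/.471/.683/.847 | .278/.374/.579/.765 |
| Fade | .083/.096/.128/.169 | .278/.374/.579/.765 |
| Month 3 only | .425/.554/.772/.912 | .358/.482/.712/.879 |

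Neither coding is always stronger. For a month-3-only effect, unadjusted linear time even exceeds the baseline-adjusted joint test (.420/.524/.731/.885).

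**Stratum.** With 15 women per stratum per arm (assumed) and no stratum effect, adding the term to the adjusted model changed simulated power by no more than 0.2 points.

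**The case against.** The strongest reply is that nothing here is an error. The interaction is unbiased, it tests improvement from baseline as Section 2 words it, and Section 15 calls the study explorative. That stands: this is a recommended improvement, not a validity defect. The largest gain also needs a sustained effect and a low correlation, and no document supports either; at rho .8 the sustained gain is 4 points.

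Several stronger readings are tempting, and the documents do not support them.
- **That the coding of time will be picked to suit the results.** Section 4 says only "The collected data will be analyzed after the data collection of all the participants is completed", which is ordinary practice. Section 5 is silent on coding. Silence leaves the choice open but does not show an intention.
- **That categorical time is the more powerful choice.** The table above shows otherwise for building and month-3-only effects.
- **That the plan ignores covariates or rules out the stratum.** Sections 2 and Phase 2 plan adjustment, the examples are open-ended, and the Section 5 list is not stated to be exhaustive. The stratum is unnamed rather than excluded, and the unfixed covariate list is a matter for clarification only.
- **That women know their group when they complete the pre-test.** Phase 2 places the questionnaire after randomisation but before log-in details are issued. Section 21 describes consent leading on to screening and the pre-test without mentioning randomisation. No section says when allocation is disclosed.

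**Conclusion.** The point holds as one of efficiency and specification. The planned interaction is valid, but for every rho below 1 it uses the collected baseline less well than adjustment would. At 30 per arm the gain for a sustained 0.5 SD effect runs from 24 points of joint power (rho .3) down to 4 (rho .8), and from 6 down to 0.6 if the effect appears only at month 3. The interval narrows at every rho examined. These sizes rest on SD 1, compound symmetry, complete data and a rho that the documents do not give. They also assume that the pre-test is a modelled response in the planned analysis and is not affected by allocation.

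Time coding should be stated because the two codings test different quantities. The stratum should be named because randomisation used it. No power gain is claimed for either.

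**What to change.** In Section 5, replace the sentence on a significant interaction with one specification:
1. Responses are the month-1 and month-3 values, with time categorical, matching the two visits named in Section 2.
2. Fixed effects are group, visit, group x visit, the baseline value of the outcome, baseline x visit, and sub-ethnic group.
3. Report the adjusted group contrast at each visit with its 95% confidence interval, and one joint 2-df test of the two contrasts.

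As a clarification, Section 5 should also carry over the covariates promised in Section 2 and Phase 2 as a short fixed list. The calculations above do not cover the degrees of freedom that list would use.

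The plan should state whether women complete the pre-test before learning their group. Until it does, it should not adopt the alternative of keeping baseline as a response with group means constrained equal, because that constraint could be false. Change scores and covariate adjustment also rely on a baseline unaffected by allocation.

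**Cost.** Wording only: the baseline outcomes and sub-ethnicity are already collected. Baseline and stratum use one or two degrees of freedom. The joint test has no direction, so direction must be read from the two contrasts. If the effect builds or appears only at month 3, a linear-time test could have had more power; that is the price of matching the stated hypotheses.

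### H1–H3 promise covariate-controlled effects, but the section 5 model places no covariates, and adding the pre-test-only ones as main effects would leave the group x time result unchanged

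*Combined protocol and SAP*

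**What the plan says.** Section 2 (Research Hypotheses) opens each of H1, H2 and H3 with the same condition. In H2, for example: "After controlling for background and health/disease factors, the intervention group will show significantly greater improvements than the control group in" the caregiving-experience outcomes. The comparison runs from baseline to 1 and 3 months.

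Section 5 (Data Analysis) gives the model for all three hypotheses: "Fixed-effects corresponding to group, time and group x time interaction will be included in the model". On random effects it says "We will use random intercepts as well as explore random slopes to represent subject level variability". The decision rests on the interaction: "A significant group x time interaction will indicate substantial differences in the groups over time". Outcomes that are missing are to be multiply imputed, and complete data are also to be analysed. Section 5 names no covariate.

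Covariates appear in the Instruments text of the procedure description (Phase 2, Aim 2): "Covariates that will be considered in determining the effect of TACAD on outcome variables include caregivers' sociodemographic characteristics and caregiving history". The examples given there are socioeconomic status, information on the person with Alzheimer's disease, length of caregiving and co-residence. The same text says these questions "will be asked only at the pre-test". The plan does not say which covariates enter which model, whether they enter alone or with time, or how they are chosen. It also does not define the health/disease factors.

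**The concern.** The hypotheses promise an adjusted comparison of improvement. The model as written has nothing that adjusts it. An analyst who notices the gap would most naturally add the listed covariates as main effects, which is how covariates usually enter a mixed model. That step looks like adjustment but does not act on the quantity being tested. The report could then describe a controlled result that is numerically the uncontrolled one.

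With 30 women per group, a noticeable chance difference in some baseline characteristic is to be expected. If that characteristic predicts change in the outcome, the difference stays in the group x time estimate, and any precision the covariate could have given is lost. Leaving list and form open also allows the choice to be made after results are seen, across many outcomes.

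**Working it through.** **The plan's own figure.** The only calculated figure is 105 per group (section 15), and this point does not depend on it. With difference 0.5, SD 1 (assumed), two-sided alpha 0.00625 and 80% power: n = 2(2.734 + 0.842)²/0.5² = 102.3, so 103 by the normal formula. A t-test with 105 per group has 80.4% power. The figure reproduces.

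**Inputs.** Three visits (section 4); 30 women per group (section 15); fixed effects of group, time and group x time (section 5); listed covariates asked at pre-test only (Instruments text).

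**Why a main effect cancels.** Write the mean for group g at visit t as μ(g,t) + βc, where c is a covariate with one value per woman. The adjusted cell mean is the raw cell mean minus β times the amount by which the group's mean of c departs from the overall mean. That correction is the same at every visit, so it drops out of follow-up minus baseline. The group x time contrast stays the raw difference in mean changes, whatever β is.

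If the coefficient may differ by visit (covariate x time), the contrast at visit t is corrected by (β_t − β_0) times the group difference in mean c. Only this form reaches the tested contrast in the three-visit model.

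**Numerical check.** REML fits to simulated data with 30 per group, three visits and three baseline-only covariates. One covariate was shifted by 0.3 SD between groups and built to predict change.

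| Setting | Shift in group x time estimate | Relative change in its SE |
|---|---|---|
| Complete outcomes, main effects; random intercept, unstructured, or random intercept plus slope | below 1e-14 SE | below 1e-7 |
| Complete outcomes, covariate x time added; random intercept or unstructured | mean 0.70 or 0.58 SE (largest 1.07) | – |
| About 20% dropout (assumed), no imputation, main effects; random intercept | mean 0.10 SE, largest 0.27 | at most 1.2% |

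The first row covers both analyses named in section 5, since imputed and complete-data sets both have three outcomes per analysed woman. The other rows illustrate the mechanism and do not predict this trial.

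**Chance imbalance.** The SD of a between-group difference in a standardised covariate is sqrt(2/30) = 0.258. The probability of a difference beyond 0.25 SD is 2[1 − Φ(0.25/0.258)], about 33%. For at least one of four independent covariates (assumed) it is 1 − 0.667⁴, about 80%.

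**Precision.** Let r be the joint correlation of the covariates with change (assumed; the documents give none). Before the cost of estimation, the SE falls by 1 − sqrt(1 − r²). With four covariates and 60 women the net SE ratio is sqrt[(1 − r²)(1 + 4/53)], where 53 = 60 − 4 − 3.

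| r | Gross reduction | Net SE ratio | Net reduction | Net, simulated |
|---|---|---|---|---|
| 0.3 | 5% | sqrt(0.91 × 1.0755) = 0.989 | 1% | 1.2% |
| 0.4 | 8% | sqrt(0.84 × 1.0755) = 0.950 | 5% | 5.0% |
| 0.5 | 13% | sqrt(0.75 × 1.0755) = 0.898 | 10% | 9.7% |

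**The case against.** Several counter-arguments have force.

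- **The plan is not silent on covariates.** Section 5 says which terms will be included, not that no others will be, and the Instruments text says "Covariates that will be considered in determining the effect of TACAD on outcome variables include" several items. A reader might infer that no adjustment is intended. The documents do not support that: adjustment is intended but unspecified and placed in no model. The main-effect form is the usual reading, not one the plan states.
- **The result can move in some circumstances.** A reader might infer that adding the covariates can never alter the interaction. That is too absolute. It can shift somewhat if incomplete outcomes are fitted directly, if women with a missing covariate drop out (participants may decline items, and only dependent values are imputed), or if covariates enter the imputation model.
- **Disease factors may be partly covered.** The list is open-ended and includes information about the care recipient, so one cannot say that health/disease factors are missing from it. What stands is that the term is undefined, and that the caregiver's other diagnosed diseases, asked at pre-test (section 32), are not named. The plan does not say whether that item is repeated, so the cancellation is established only for the sociodemographic and caregiving-history items.
- **The harm is limited.** The interaction already removes anything that shifts a woman's three scores equally. Under randomisation, remaining imbalance is chance error reflected in the standard error, not bias. The trial is a 60-woman pilot described as exploratory.

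These points bound the concern. They do not remove the mismatch between the adjusted hypotheses and a model that does not adjust the tested contrast.

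**Conclusion.** The point holds in a bounded form. The section 5 model does not deliver the control that H1–H3 promise, and the obvious repair leaves the group x time estimate and test unchanged in both analyses the plan names. This rests on covariates with one value per woman and on three observed or imputed outcomes for each woman analysed. With incomplete outcomes fitted directly, the shift was small in the check.

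A reader might go further and conclude that the trial's comparison is biased or invalid. The documents do not support that: allocation is random within sub-ethnic group, and the unadjusted test remains valid. The loss is control of chance imbalance in predictors of change and a net reduction in standard error of roughly 1% to 10%, under assumed correlations of 0.3 to 0.5 and four covariates. The plan should be changed before data are seen, but the point does not threaten the trial.

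**What to change.** State in section 5 that a short list of baseline covariates, fixed before data are seen, acts on the treatment contrast, in one of two ways:

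1. Model the 1-month and 3-month scores, adjusted for the baseline score of the same outcome, sub-ethnic group (the randomisation stratum) and the listed covariates. The baseline score is essential, because the hypotheses concern improvement from baseline. This form also fits the section 15 target, a difference in group means over follow-up, which baseline main effects do adjust.
2. Keep the three-visit model and add covariate x categorical-time terms.

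Keep the list to about two to four items, for example length of caregiving, co-residence and one health/disease item already asked at pre-test. Say which items are the health/disease factors in H1–H3.

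The cost is a few sentences, no new data and a few degrees of freedom per outcome. The upper end is option 2 with four single-parameter covariates: 4 × (1 main effect + 2 time terms) = 12 parameters per outcome, which is a reason to keep the list short with 60 women.
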